## **5.3 Treatment Duration and Study Visits**

The treatment duration will be 12 weeks. Patients will receive PD treatment, as prescribed, in their home throughout the duration of the study. After patients have completed the  $Kt/V_{\text{urea}}$  assessment required during Week 5, 6, 7 or 8 of the Study Treatment Period, in order to accommodate potential vacation/travel, they may voluntarily interrupt investigational AMIA APD Solution Generation System treatment and perform standard of care PD therapy using the marketed AMIA or HomeChoice APD Cycler with currently available PD solution (e.g. Dianeal) up to 2 separate times with prior approval from the Investigator for up to 14 days in total; however, patients must complete a total of 12 weeks of cumulative therapy using the AMIA APD Solution Generation System. If required, per patient prescription and if the patient has been treating with premixed Extraneal prior to study enrollment, premixed Extraneal may be used for the last fill.

Baseline assessments will occur during the Baseline Period (In-Center Training Period) before patients initiate treatment with the AMIA APD Solution Generation System (See Section 8.4 for details of assessments occurring at Baseline).

---

Simulated treatments will occur in addition to the patient's normal therapy regimen. The simulated treatment will take place before the patient receives study treatment. The initial simulated treatment will occur before the first treatment in the home with the AMIA APD Solution Generation System, Study Treatment Week 1 (Study Visit 1). Simulated treatments will continue during Study Treatment Weeks 4 (Study Visit 2), 8 (Study Visit 3) and 12 (Study Visit 4). Patients will be required to use new AMIA APD Concentrates and disposable sets for their treatment, following a simulated treatment.

The dialysis solution generated by the simulated treatment will be collected from the system in the heater bag and used to evaluate the chemical composition of the final dialysis solution produced by patients using the AMIA APD Solution Generation System, compared to the specifications of Baxter's approved Dianeal Low Calcium (2.5 mEq/L) PD Solution.

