### **8.9 Follow-up Period**

After the last study treatment with AMIA APD Solution Generation System, patients will transition back to Standard AMIA treatment with Baxter's approved Dianeal Low Calcium (2.5 mEq/L) PD Solution and enter a Follow-up Period of 5-10 days. During this time, an assessment by an Investigator or a designee will occur. At a minimum, this assessment will include evaluation of BP, pulse rate, weight, fluid status and dialysis prescription. Adverse events, SAEs, ADEs and SADEs will be collected throughout the Follow-up Period and through the End-of-Study/ Early Termination Visit.

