4.2 Secondary Objectives

- To evaluate the safety of the AMIA APD Solution Generation System, used to treat patients with ESRD, by collecting adverse events (AEs), serious adverse events (SAEs), adverse device effects (ADEs), serious adverse device effects (SADEs), incidence of device alarms and vital signs.
- To assess PD adequacy by calculation of total Kt/V_{urea} .

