11. TREATMENT COMPLIANCE AND EXPOSURE

11.1 Treatment Compliance

Compliance will be assessed regularly by the Investigator by reviewing the patient's Sharesource Platform data and eDiary entries. The patient will be instructed to complete the eDiary daily to document treatment activities including, but not limited to, the following:

- Treatment interruptions
 - Confirmation if the patient contacted dialysis center for support with a product or health-related issue
 - Confirmation if the patient was able to sleep during treatment
-
- 

- Treatment outcome (i.e., complete treatment, incomplete treatment) and reasons for incomplete treatment
- Confirmation if the patient altered their treatment parameters
- Investigational product supply requirements

The above eDiary data (with the exception of the investigational product supply requirements) will be summarized using frequencies and percentages for the number of patients experiencing at least one event and the total number of events per total treatments, and it will be summarized continuously using mean, standard deviation, minimum, median, and maximum for the total number of occurrences per patient. These data will also be listed.

For patients who have re-enrolled, the eDiary data will be pooled together.

Interruptions to therapy will be summarized using frequencies and percentages of the following:

- Number of interruptions per patient
- Reason for interruption
- Whether the patient was on standard of care PD therapy

The length of treatment interruption for all interruptions as well as per patient will be summarized for all interruptions using n, mean, median, standard deviation, minimum, and maximum.

The length of treatment interruptions for all interruptions will be calculated as follows:

$$\frac{\sum_{i=1}^t (\text{Treatment restart date} - \text{Date of interruption})}{t},$$

where i is each interruption and t is the total number of interruptions.

The length of total treatment interruptions per patient will be calculated as follows:

$$\frac{\sum_{i=1}^n \sum_{j=1}^m (\text{Treatment restart date} - \text{Date of interruption})}{n},$$

where j is each interruption per patient, m is the total number of interruptions per patient, i is each patient, and n is the total number of patients with an interruption.

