14.2 Adverse Events (AEs)

14.2.1 General

Summaries of AEs will be presented using counts and percentages for the safety set.

Tables by preferred term and tables by system organ class (SOC) and preferred term will be sorted in descending order by the percentage of patients.

For all adverse event analyses, the date of first treatment will refer to the first date the patient ever received treatment with the Point of Care device. If a patient had stopped treatment then re-started, the date that they first started (including prior enrollments) will be used as the date of first treatment.

Unless otherwise specified, the summaries of adverse events will include the total number of patients experiencing the adverse event, the total number of events, and the adverse event rate (number of events per patient year). The total number of patient years will be calculated as follows for all adverse events (including pretreatment AEs):

$$\frac{\sum_{i=1}^n (\text{Date of Study Completion/Withdrawal} - \text{Informed Consent Date}) + 1}{365.25},$$

where n represents all patients in the Safety Set.

The total number of patient years will be calculated as follows for all treatment-emergent adverse events:

$$\frac{\sum_{i=1}^n (\text{Date of Study Completion or Withdrawal} - \text{Date of first treatment}) + 1}{365.25},$$

where n represents all patients in the Safety Set.

The adverse event rate will be calculated as:

$$\frac{\text{Total Number of Events}}{\text{Total patient years}}$$

For summaries of AEs presented by severity, the maximum severity will be presented if patients have multiple AEs within a SOC and preferred term (PT) with varying severity. If the severity of an adverse event is missing, then that adverse event will be classified as *severe*.

For summaries of AEs presented by relationship, the most conservative relationship will be presented if patients have multiple AEs within a SOC and PT with different relationships to either study product or typical PD therapy.

For patients who had re-enrolled, all adverse events will be listed and summarized.

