14.2.2 Classification of Adverse Events

Pre-treatment adverse event – An adverse event that starts between the date of signing the informed consent form (ICF) and the start of the first treatment.

Treatment-emergent adverse event (TEAE) – An adverse event that starts on or after the start of the first treatment.

In case of incomplete information on study treatment or AE onset, events will be classified as treatment-emergent unless there is sufficient data to rule out the possibility that the event started after the start of study treatment application.

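### SAP 14.2 pools events and time on the study system with time on marketed PD, with no flag for therapy at onset; device-related rates per patient-year may therefore print low

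*SAP*

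**What the plan says.** SAP 14.2.2 defines a treatment-emergent adverse event (TEAE) as "An adverse event that starts on or after the start of the first treatment". There is a start but no end, and no condition about which therapy is in use. SAP 14.2.1 sets the denominator to match: "The total number of patient years will be calculated as follows for all treatment-emergent adverse events", and the formula runs from first treatment to "Date of Study Completion or Withdrawal", plus one, with no deduction for days off the system. The same section makes an event rate per patient-year a default part of AE summaries.

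Two features of the design put patients on another therapy while they remain under AE collection:

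- **Travel breaks.** Under Protocol 5.3, once the Kt/V assessment is done, patients may switch to a marketed cycler and available solution "up to 2 separate times with prior approval from the Investigator for up to 14 days in total". The 12 weeks on the study system must still be reached cumulatively.
- **Follow-up.** Under Protocol 8.9, after the last study treatment "patients will transition back to Standard AMIA treatment with Baxter's approved Dianeal Low Calcium (2.5 mEq/L) PD Solution" for 5 to 10 days. AEs, SAEs, ADEs and SADEs are all collected in that time.

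The secondary safety objective in SAP 4.2 is "To evaluate the safety of the AMIA APD Solution Generation System, used to treat patients with ESRD". SAP 11.1 already summarises interruptions from their start and restart dates, including "Whether the patient was on standard of care PD therapy". SAP 14.3.2 uses a different denominator for alarms and device deficiencies: days from home installation to last treatment.

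**The concern.** The reader of the safety tables wants to know what happens while patients use the study system. As written, an event that begins on a marketed cycler during a trip, or on Dianeal in Follow-up, enters the same TEAE tables as one that begins on the system, and those days enter the same patient-years. Because the 12 weeks are cumulative, a break lengthens the denominator without adding any system exposure.

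Days on standard PD probably bring little new device-related risk. If so, the rates for study-device-related TEAEs and SAEs (Tables 14.3.1.1.4 and 14.3.1.1.7) come out too low. The therapy being mixed in is also the one the study solution is meant to match in composition (Protocol 3.3) and is expected to match in safety (Protocol 1.2), so pooling blurs the system's own profile.

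The SAP is also uneven. A deficiency that results in an AE is rated on time that stops at last treatment, while the AE itself is rated on time that includes Follow-up. The AE listing fields in SAP 14.2.1 give the treatment start date but not the therapy at onset, the last treatment date or the interruption dates. A reader would have to cross-match against Listing 16.2.6.4.

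**Working it through.** **The plan's own duration.** Screening 3 weeks, Baseline 2 weeks, treatment 12 weeks and follow-up 5 to 10 days (Protocol 3.4) give 3 + 2 + 12 + 5/7 = 17.7 to 3 + 2 + 12 + 10/7 = 18.4 weeks. This reproduces the stated 18 weeks or so. Travel breaks are not in that total; 14 days of them would make it 19.7 to 20.4 weeks.

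**Inputs for a completer.** On-system time is 12 x 7 = 84 days. Travel break is 0 to 14 days (Protocol 5.3). Follow-up is 5 to 10 days (Protocol 8.9); the SAP visit-window table says 5 days, which lies at the low end of that range.

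**Formulas.** Off = break + follow-up. Off-system share = off / (84 + off). If no device-related event starts off system, the printed rate is below the on-system rate by exactly this share, and the on-system rate is (84 + off) / 84 times the printed one.

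| Break (days) | Follow-up (days) | TEAE days | Off-system share | On-system / printed rate |
|---|---|---|---|---|
| 0 | 5 | 89 | 5/89 = 5.6% | 1.060 |
| 0 | 10 | 94 | 10/94 = 10.6% | 1.119 |
| 14 | 5 | 103 | 19/103 = 18.4% | 1.226 |
| 14 | 10 | 108 | 24/108 = 22.2% | 1.286 |

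**If some device-related events start off system.** Let k be the off-system event rate divided by the on-system rate (an assumption). Printed / on-system = (84 + k x off) / (84 + off).

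| k | off = 5 | off = 10 | off = 24 |
|---|---|---|---|
| 0 | 0.944 | 0.894 | 0.778 |
| 0.5 | 0.972 | 0.947 | 0.889 |
| 1 | 1.000 | 1.000 | 1.000 |
| 1.5 | 1.028 | 1.053 | 1.111 |

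The dilution halves at k = 0.5, disappears at k = 1 and reverses above 1. For all-cause TEAEs nothing in the documents fixes k, so the direction is open.

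**Whole cohort, follow-up averaging 7.5 days (assumed).** For 30 completers with no breaks the share is 7.5/91.5 = 8.2%. If one third take 14 days (assumed), average off time is 7.5 + 14/3 = 12.17 days and the share is 12.17/96.17 = 12.7%. Adding 20 early leavers with a mean of 28 to 42 days on system (assumed, each with the 7.5-day tail) gives 375/3455 = 10.9% to 375/3735 = 10.0% without breaks. With one third of completers taking breaks it gives 515/3595 = 14.3% to 515/3875 = 13.3%.

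**Scale against sampling error.** Suppose 10 device-related events, all on system, in 30 completers (assumed). On-system patient-years are 30 x 84/365.25 = 6.90, a rate of 1.45. Under the SAP the patient-years are 7.31 to 8.87 and the rate 1.37 to 1.13. The exact Poisson 95% interval for 10 events is about 0.48 to 1.84 times the estimate.

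**The case against.** Several points on the other side stand.

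- **Only the person-time rate is diluted.** Protocol 10.6 plans frequencies and percentages, and SAP 14.2.4 lists patients, percentages and event counts. The rate enters through the default in SAP 14.2.1. Nothing in 14.2.4 switches that default off, so the rate is still planned, but it is not the main presentation.
- **Counting events through a short follow-up is a normal safety convention.** It catches late-presenting events, and Protocol 8.9 collects ADEs and SADEs there on purpose. The objective sets no on-system window. A reader might infer that the planned rates answer a different question from the objective. The documents do not support that for Follow-up; the argument is stronger for travel breaks.
- **Being a TEAE is not attribution.** Each event is separately classified by relation to the study device, typical PD therapy or another Baxter product. A reader might infer that events on the marketed cycler are credited to the study system. They are pooled in the TEAE tables, but the relationship tables do not assign them to the device.
- **The larger figures need particular conditions.** The 22.2% needs both the full break and the longest follow-up. Early leavers could show more: 5/19 = 26% to 10/24 = 42% for someone stopping after 14 days. That requires the withdrawal date to fall after the follow-up tail. SAP 14.2.1 does not define that date, and SAP 7.3 foresees patients who never return. No document gives break uptake or withdrawal timing.
- **No stated decision depends on the rate.** The study is descriptive and single-arm, with no rate threshold, and sampling error exceeds the shift.

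What remains is that two therapies are pooled with nothing to separate them.

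**Conclusion.** The point holds in a limited form. SAP 14.2.1 and 14.2.2 mix the study system with observed time on marketed PD, and the reader cannot tell which therapy an event began on. Counts and percentages are not diluted, though they include off-system onsets. For a completer, and provided device-related events start only on system, the printed device-related rate is 5.6% to 10.6% below the on-system rate with no break, and up to 22.2% below with the full 14-day break and 10-day follow-up. The cohort figures above rest on assumed break uptake, follow-up length and time to withdrawal, and should be read as illustrations.

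A reader might go further and conclude that the device-related rates are necessarily biased low. The documents do not establish this: it depends on few such events starting off system, and the plan collects them there. The effect is modest and on a secondary descriptive summary, but it is cheap to make visible.

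**What to change.** Keep the TEAE definition and all existing tables and rates. Then:

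1. **SAP 14.2.2:** flag each TEAE by status at onset: on the study system; in an interruption, with or without standard-of-care PD; or in the Follow-up Period. Show the flag in the AE listings and add a split line to Table 14.3.1.1.1.
2. **SAP 14.2.1:** for study-device-related TEAEs and SAEs (Tables 14.3.1.1.4 and 14.3.1.1.7), add an on-system rate beside the planned one. The numerator is events starting on system. The denominator is on-system patient-years: last minus first system treatment date plus 1, minus the interruption days captured for SAP 11.1, summed over patients and divided by 365.25.
3. **Late events:** report device-related events starting in an interruption or in Follow-up on a separate line, so that none is lost.

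Numerator and denominator must cover the same window. Keeping device-related events of any onset over on-system time alone would push the rate up through mismatch, and should be avoided. For a re-enrolled patient, the SAP should also state that the gap between enrolments is not on-system time.

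The dates are already used in SAP 11.1 and 14.3.2. The cost is one derived variable, some SAP wording, and a second rate to footnote that will usually print somewhat higher.

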14.2.3 Adverse Events of Special Interest (AESI)

In this study, AESIs are defined as any of the following events:

- Aseptic Peritonitis
 - Hypovolemia
 - Hypokalemia
 - Hyponatremia
 - Encapsulating Peritoneal Sclerosis
 - Medication Error: administration of incorrect glucose concentration
 - Lactic Acidosis
 - Hyperglycemia
-
- 

- Hypocalcemia

14.2.4 Presentation of Adverse Events

An AE overview summary table will be prepared to include the number of patients reporting an AE, the percentage of patients (%) with an AE, the number of events reported, for the following categories:

1. Any treatment emergent adverse event
2. Treatment-emergent SAEs.
3. Treatment-emergent pre-defined AEs of special interest
4. Treatment-emergent study device-related AEs.
5. Treatment-emergent typical PD-related AEs
6. Treatment-emergent study device-related SAEs
7. Treatment-emergent typical PD-related SAEs
8. Treatment-emergent AEs leading to withdrawal.
9. Treatment-emergent AEs leading to death.

Adverse events will be further tabulated by body system using the MedDRA coded values. The table will display the total number of patients reporting an AE, the percentage of patients (%) with an AE, and the number of events reported by overall, system organ class (SOC), and preferred term. Table summaries will be produced for:

- All treatment-emergent AEs
 - Treatment-emergent AEs leading to withdrawal
 - Treatment-emergent SAEs
 - Treatment-emergent AEs leading to death
 - Treatment-emergent pre-defined AEs of special interest
 - Treatment-emergent pre-defined SAEs of special interest
 - Treatment-emergent AEs by severity
 - Treatment-emergent SAEs by severity
-
- 

- Treatment-emergent AEs by relationship to study product
- Treatment-emergent SAEs by relationship to study product
- Treatment-emergent AEs by relationship to typical PD therapy
- Treatment-emergent SAEs by relationship to typical PD therapy
- Treatment-emergent adverse events in $\geq 5\%$ of patients

Adverse events occurring between informed consent and treatment start (pre-treatment AEs), treatment-emergent adverse events, treatment-emergent SAEs, treatment-emergent adverse events leading to withdrawal, treatment-emergent adverse events related to study device, typical PD therapy, or another Baxter product, and adverse events for patients who died will be listed.

For the SAE listing, the seriousness criteria will also be included in the listing.

If there are less than 5 adverse events in one of the bulleted categories above, then a listing may be created instead of a table for those AEs.

14.3 Other Safety Data

14.3.1 General

Unless otherwise specified, tables, listings, and figures will be based on the Safety Set.

14.3.2 Device Alarms and Device Deficiencies/Product issues (DDs)

All device deficiency tables and listings will be done on the Safety Set. The number of device alarms and their relation to AEs will be summarized using frequency counts and percentages. The number of patients experiencing at least one device alarm and at least one device alarm due to an AE will also be summarized. Included in this summary will also be the number of patients experiencing at least one DD/product issue and at least one DD/product issue resulting in an AE, suspected unexpected serious adverse reaction (SUSAR), or unexpected adverse drug reaction (UADE). All of the above will also be summarized as a rate of events per total device installation days. This rate will be calculated by taking the number of events and dividing it by the total number of days the device is installed at a patient's home across all patients. The total number of device days will be calculated as follows:

$$\sum_{i=1}^n (\text{Date of last treatment} - \text{Date of home installation}) + 1,$$

where i is each patient and n is the total number of patients in the Safety Set.

All device deficiencies and product issues will be summarized by frequencies and percentages of both patients and total events, and by a rate of events per total number of device installation days for the following:

- Product causing DD
- Type of deficiency/product issue
- Occurrence of DD
- Whether the device gave an alert, alarm, or error message
- If there was a safety concern
- If the DD resulted in an AE or SUSAR/UADE

A listing will also be provided for all device deficiencies/product issues sorted by site ID, patient ID, and DD date. It will provide the product affected, date of onset, type, description, occurrence, whether a message was given (alert, alarm, error, or none), message description, if/what is a potential safety concern, and if/what AE resulted because of this DD.

For patients who had re-enrolled, all DDs will be listed and summarized.

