7.2 Analysis Populations

The Safety Set is based on the intent-to-treat principle and will include all patients who have received at least one treatment with the AMIA APD Solution Generation System and who have at least one measurement for the primary endpoint (either primary efficacy or primary safety).

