7.3 Completion and Discontinuation

A patient who withdraws from the study prior to meeting all eligibility criteria or prior to having the device installed in their home will be considered a screen failure. All withdrawals past this point will be considered a withdrawal and be counted as a

discontinuation. In the event that a patient has a home installation and has not yet met all eligibility criteria but decides to withdraw from the study due to a device issue (i.e. leaking, alarms, etc.), then the patient will be considered as discontinued and NOT as a screen failure.

A patient is considered to have completed the study when he/she ceases active participation in the study because the patient has, or is presumed to have, completed all study procedures according with the protocol (with or without protocol deviations). Any other cases are classified as discontinuation.

Reasons for completion/discontinuation will be reported on the Completion/Discontinuation electronic case report form (eCRF), including:

- Adverse event
- Change to another dialysis center
- Death
- Disease progression
- Home feed water affected by boil water advisory
- Inadequate dialysis
- Investigator discretion
- Lost to follow-up
- Met an exclusion criteria
- Missed more than 4 consecutive days of therapy
- Consistently missed more than 1 prescribed treatment per week
- Pregnancy
- Protocol violation
- Renal transplant
- Termination of the study
- Voluntary withdrawal
- Water device replacement
- Other

Regardless of the reason, all data available for the patient up to the time of completion/discontinuation should be recorded on the appropriate eCRF.

Every effort will be made to have discontinued patients complete the study completion/termination visit. If the completion/termination visit is done as an additional, unscheduled visit, the assessment results shall be recorded with the completion/termination visit. If a patient terminates participation in the study and does not return for the completion/termination visit, his/her last recorded assessments shall remain recorded with his/her last visit. The reason for discontinuation will be recorded and the data collected up to the time of discontinuation will be used in the analysis and included in the clinical study report.

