Patients who discontinue may be allowed to reenroll in the study. These patients will have separate but linked patient IDs (one for each enrollment in the study); this will be captured in the eCRF. These patients will be assigned one unique USUBJID during SDTM creation. Unless otherwise specified, for all patient-related analyses (e.g. demographics and baseline characteristics), these data will be summarized only once in tables, and all data will be listed next to their corresponding USUBJID in listings. For all device-related analyses (e.g. chemical composition testing of dialysis solution, microbiological testing of product water), all data gathered will be summarized and listed.

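### SAP 14.3.2 leaves deficiencies on systems installed for never-treated patients out of every device-deficiency output, and its device-day formula stops short of the installed days that its text defines

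*SAP*

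**What the plan says.** **Population.** SAP 14.3.2 opens: "All device deficiency tables and listings will be done on the Safety Set". SAP 7.2 defines that set to "include all patients who have received at least one treatment with the AMIA APD Solution Generation System and who have at least one measurement" of a primary endpoint.

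**Withdrawal before treatment.** SAP 7.3 considers a patient who "has a home installation and has not yet met all eligibility criteria but decides to withdraw from the study due to a device issue", giving leaks and alarms as examples, and rules that "the patient will be considered as discontinued and NOT as a screen failure". Protocol 8.10 calls the same patient an Early Termination patient. Protocol 6.8 says that all available data from patients removed early enter all analyses, and SAP 7.3 says much the same.

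**Re-enrollment.** SAP 7.3: "These patients will be assigned one unique USUBJID during SDTM creation". SAP 14.3.2: "For patients who had re-enrolled, all DDs will be listed and summarized".

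**Rate.** The SAP 14.3.2 text obtains the rate by taking the number of events and "dividing it by the total number of days the device is installed" at a patient's home. The formula below it runs from home installation to "Date of last treatment", plus 1, summed over the Safety Set.

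**Collection window.** Protocol 7.2 documents deficiencies from consent through the End-of-Study or Early Termination Visit, and Appendix 1 footnote w says through the entire Study Period. Protocol 8.5 item 6 ends collection with the Study Treatment Period. The Appendix 1 grid marks the deficiency row only at Simulated Treatment Visit 1 and on each treatment day.

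**The concern.** This study asks whether the system works in patients' homes. A system abandoned over leaks or alarms before its first treatment bears directly on that question. The plan counts the patient as a discontinuation, then reports device deficiencies on a population that the patient cannot enter. The omission favours the device.

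The rate has a different problem: one quantity has two definitions. If the device stays in the home after the last treatment, the formula gives fewer days than the text promises, and the rate per installed day is overstated. The two faults pull in opposite directions, so the net effect is not known in advance.

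**Working it through.** The plan states no deficiency rate or count, so there is no figure to reproduce.

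**Who is lost**

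1. All deficiency tables and listings use the Safety Set (SAP 14.3.2), and membership needs at least one treatment (SAP 7.2). A patient never treated is in none of Tables 14.3.6.1-14.3.6.2 or Listings 16.2.12.1-16.2.12.5.
2. The exclusion works by patient. Someone who leaves untreated, re-enrolls and is then treated has one USUBJID, and all of that person's deficiencies are kept. Only patients never treated in any enrollment are lost.
3. Such a patient can have a deficiency on record. Documentation starts at consent (Protocol 7.2). Installation and water testing take about two weeks (Protocol 4.4), and home treatment must wait for the post-installation water results (Protocol 6.5.8.1 and 6.5.8.2). Every installed system therefore passes through an untreated period.
4. Disposition does not fill the gap. The withdrawal listing covers everyone who consented and gives the primary reason, not the deficiency record. The summary by reason is specified only for patients who re-enrolled (SAP 7.1).
5. The SAP does widen other listings. Those for dialysis solution, product water, holding-bag water and feed water include all enrolled patients (SAP 13.2, 14.1.2, 14.1.3, 14.3.5).

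**Device-days for one completer**

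Inputs: 12 weeks of treatment = 84 days, without interruption. Product return is scheduled in the Follow-up Period (Protocol 8.7), which lasts 5-10 days (Protocol 3.4), so return is taken as 1 to 10 days after last treatment. Assumption: installation 14 days before first treatment, or 35 days if it falls at the start of the roughly 3 + 2 weeks of Screening and Baseline. The plus 1 is read as per patient.

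Formula days = lead + 84. Installed days = formula days + days to return. Overstatement = installed days / formula days - 1.

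| Lead | Formula days | Installed days | Overstatement |
|---|---|---|---|
| 14 | 14 + 84 = 98 | 99 to 108 | 99/98 - 1 = 1.0% to 108/98 - 1 = 10.2% |
| 35 | 35 + 84 = 119 | 120 to 129 | 120/119 - 1 = 0.8% to 129/119 - 1 = 8.4% |

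**Effect of one omitted patient on the pooled rate**

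Thirty completers give 30 x 98 = 2,940 formula days. One untreated patient with 14 installed days adds 14/2,940 = 0.5%. If each completer had one deficiency (an assumption), adding one event changes the rate from 30/2,940 = 1.02 to 31/2,954 = 1.05 per 100 device-days, or 2.8%. With fewer events overall the shift would be larger.

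**The case against.** **The listing sentence.** SAP 14.3.2 later promises a listing of all device deficiencies, which could be read as covering everyone. The opening sentence of the section governs all of its listings, however, and SAP 14.3.1 repeats the Safety Set default. The general statements in Protocol 6.8 and SAP 7.3 show intent but name no output that would carry these records.

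**Disposition.** A withdrawal classed as other must have its reason noted (Protocol 3.5.1), so an exit caused by the device may be recognisable in the withdrawal listing. That stands, but it is not the deficiency record.

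**Importance.** Deficiencies are not a named endpoint, and the study is descriptive. That limits the consequence and leaves the primary tables untouched.

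**Stronger readings that the documents do not support.**

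- A reader might infer that deficiencies are certainly counted after the denominator ends. Protocol 7.2 and footnote w point that way; Protocol 8.5 item 6 and the Appendix 1 grid point the other way. If collection stops with treatment, events and days end together. The conflict between text and formula remains either way.
- A reader might size the omission from the cap of 50 and the target of 30 completers. Those figures count enrolled patients, and SAP 7.1 defines enrolled as installed and fully eligible. The patient in SAP 7.3 who leaves before eligibility is confirmed is outside that count. The documents set no bound on the number installed.
- A reader might say that the formula fails for untreated patients because they have no last treatment. It sums over the Safety Set only, so as written they never enter it. The difficulty arises only when the population is widened.

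**Conclusion.** The point holds on two counts. Followed as written, the SAP omits from every deficiency table and listing any deficiency on a system installed for a patient never treated in any enrollment, a case that both documents anticipate. How many patients this affects cannot be derived from the documents. The loss is chiefly in patient counts and listings; the pooled rate moves little unless deficiencies are rare.

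In addition, the text and the formula for device-days disagree. For the same events, the rate per installed day is about 1% to 10% too high with a 14-day lead and about 1% to 8% with a 35-day lead. Both ranges rest on the assumed lead, 84 uninterrupted treatment days and return on any of days 1 to 10 after last treatment. Whether events can also fall after the denominator ends is open until the collection passages are reconciled.

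**What to change.** - Run the deficiency parts of Tables 14.3.6.1-14.3.6.2 and Listings 16.2.12.1-16.2.12.5 on all patients with a home installation, with a Safety Set version alongside if wanted. Do not use enrolled as defined in SAP 7.1, since it would still miss the SAP 7.3 case.
- SAP 14.3.2 puts alarms and deficiencies in one summary. Split it: keep device-alarm summaries on the Safety Set, as Protocol 10.6 has them, with their own denominator.
- Count device-days from installation to de-installation within each enrollment, using withdrawal or study end where the de-installation date is not recorded. State that the plus 1 applies per patient and enrollment.
- Reconcile Protocol 7.2 and footnote w with Protocol 8.5 item 6 and the Appendix 1 grid, and make the event window match the device-days.

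The analysis change needs SAP wording and one population flag. Protocol 10.6 sets no population for deficiencies, so no protocol analysis section has to change; only the collection-window wording does. A de-installation visit is already planned for feed-water sampling (Protocol 6.5.8). The downside is one more set of tables if both versions are kept, and more patients may be shown with a deficiency.
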